6.13.2. Prohibited Medications and Non-Drug Therapies

The following concomitant medications or therapies are not permitted at any time during the study:

- HIV immunotherapeutic vaccines are not permitted at any time during the study.
- Other experimental agents, antiretroviral drugs not otherwise specified in the protocol, cytotoxic chemotherapy, or radiation therapy may not be administered (see Exclusion Criteria #35-36, Section 5.2).
- Systemically administered immunomodulators (such as interleukin and interferon agents) are prohibited (a list of examples is provided in the SPM). This includes topical agents with substantial systemic exposure and systemic effects. Use of topical imiquimod is permitted.

- Acetaminophen (paracetamol) cannot be used in patients with acute viral hepatitis (James, 2009).
- Chronic use of systemic (oral or parenteral) glucocorticoids must be avoided due to their immunosuppressive effect; however, short treatment courses with oral prednisone/ prednisolone/methylprednisolone (e.g. adjunctive treatment of *Pneumocystis pneumonia* with ≤ 21 days of tapering prednisone) are allowed. A single dose of systemic dexamethasone is permitted (more than a single dose in a treatment course may cause significant decrease in RPV plasma concentration and is prohibited). Topical, inhaled or intranasal use of glucocorticoids will be allowed.
- Hepatitis C infection therapy is prohibited during the Maintenance Phase before the Week 48 primary endpoint, and interferon-based HCV therapy or use of any drugs that have a potential for adverse drug:drug interactions with study treatment is prohibited throughout the entire study.

For information on concurrent therapies and interactions suspected to be relevant to other antiretroviral therapy in the regimen, please consult the local prescribing information.

6.13.2.1. Concurrent with CAB and/or RPV

For participants receiving **either formulation** of CAB and/or RPV, the following medications could significantly decrease the levels of CAB and/or RPV due to enzyme induction and therefore must not be administered concurrently:

- Carbamazepine
- Oxcarbazepine
- Phenobarbital
- Phenytoin
- Rifabutin
- Rifampicin / Rifampin
- Rifapentine
- St. John's wort (*Hypericum perforatum*)

Concurrent with CAB

CAB is a potent inhibitor of OAT1 and OAT3 transport in vitro, however, no clinically significant interaction risk is expected for most drugs that are substrates of these transporters. Monitoring may be required for drugs with a narrow therapeutic index and dependent on OAT1 and OAT3 transport (e.g. methotrexate) with concomitant CAB administration. Refer to the current Investigator's Brochure (Section 4.3.6.1 and Section 6.4) for additional information.

Concurrent with RPV

In addition, participants must discontinue the following (or change to an allowable alternative) while receiving treatment with oral RPV:

- proton pump inhibitors, such as esomeprazole, lansoprazole, omeprazole, pantoprazole, rabeprazole;

- systemic dexamethasone (more than a single dose)

If the participant cannot discontinue use or change to an allowable alternative while receiving treatment with RPV, the participant should not be randomized into the study.

6.13.2.2. Concurrent with either CAB LA or RPV LA

In addition, for participants receiving CAB LA and RPV LA, use of anticoagulation agents for greater than 14 days is prohibited, with the exception of the use of anticoagulation for deep vein thrombosis (DVT) prophylaxis (e.g., postoperative DVT prophylaxis) or the use of low dose acetylsalicylic acid (≤ 325 mg). Systemic anticoagulation (including prophylaxis doses) on the day of an IM injection should be avoided.

Note: Any prohibited medications that decrease cabotegravir or rilpivirine concentrations should be discontinued for a minimum of four weeks or a minimum of three half-lives (whichever is longer) prior to the first dose and any other prohibited medications should be discontinued for a minimum of two weeks or a minimum of three half-lives (whichever is longer) prior to the first dose.

6.13.2.3. Prohibited Medications for Participants Receiving HAART during the Long-Term Follow-Up Phase

For participants taking HAART during the Long-Term Follow-Up Phase, refer to local prescribing information for details regarding concurrent therapies.

7. STUDY ASSESSMENTS AND PROCEDURES

Protocol waivers or exemptions are not allowed with the exception of immediate safety concerns. Therefore, adherence to the study design requirements, including those specified in the Time and Events Table, are essential and required for study conduct.

This section lists the procedures and parameters of each planned study assessment. The exact timing of each assessment is listed in the Time and Events Table (Section 7.1).

The following points must be noted:

- If assessments are scheduled for the same nominal time, THEN the assessments should occur in the following order:
 1. 12-lead ECG
 2. vital signs
 3. blood draws

Note: The timing of the assessments should allow the blood draw to occur at the exact nominal time.

- The timing and number of planned study assessments, including safety, pharmacokinetic, pharmacodynamic/biomarker assessments may be altered during the course of the study based on newly available data (e.g., to obtain data

- closer to the time of peak plasma concentrations) to ensure appropriate monitoring.
- The IRB/IEC will be informed of any safety issues that require alteration of the safety monitoring scheme or amendment of the Informed Consent Form.

7.1. Time and Events Table

Note: While some assessments included in the Time and Events Table are conducted less frequently following the primary endpoint (Week 48), IM injections for participants during the Extension Phase will continue to be administered Q4W or Q8W based on original study randomization assignment.

All patients will be randomized at Day 1 to initiate either Q4 weekly or Q8 weekly administration of IM CAB LA + RPV LA. Only participants randomized from oral SOC treatment will participate in the Day 1 to Week 4 Oral CAB + Oral RPV lead-in treatment.

- h. A 12-lead ECG will be performed after resting in a semi-supine position for at least 5 minutes. ECGs will be performed pre-dose. For participants transitioning from ATLAS, the pre-dose Week 48 ECG can also serve as the ATLAS-2M Screening ECG. ECG pre-dose will be performed in triplicate at Day 1. A 2-hour post-dose ECG will also be performed at Days 1 and Week 48 for participants receiving CAB LA + RPV LA with an allowable window of ± 30 minutes.
- i. Only SAEs related to study participation or to a concomitantly administered ViiV/GSK product will be collected between obtaining informed consent and administration of study drug at Day 1.
- j. On Day 1, the eC-SSRS is to be administered prior to randomization. The eC-SSRS will preferably be completed at the beginning of the visit following administration of other PROs required prior to injections. The eC-SSRS is not required during the Withdrawal visit if withdrawal occurs during the Extension Phase.
- k. Women of childbearing potential only. SR=serum, UR=urine. Pregnancy events will be captured starting at Day 1 following initial exposure to study drug. Urine pregnancy test performed at Day 1 prior to administration of study drug, at Week 4b, and at study visits when other blood draws are not required in order to limit needle sticks. Serum pregnancy test can substitute for urine pregnancy test if locally required but must be appropriately timed to confirm pregnancy status prior to randomization and first IM administration.
- l. Week 48 and Week 96 HIV-1 RNA retest (within 4 weeks) for results > 50 c/mL will be captured as unscheduled visit. Plasma for storage samples will be used for possible future analyses.
- m. A morning specimen is preferred. To assess biomarkers: urine albumin/creatinine ratio; urine protein/creatinine ratio; and urine phosphate. Urine phosphate results from visit 4a are not required by protocol to inform the safety review at visit 4b prior to receipt of initial CAB LA + RPV LA injections.
- n. An overnight fast is preferred; however, a minimum of a 6-hour fast is acceptable.
- o. Only collect if the Withdrawal visit occurs at Week 48 or Week 96.
- p. Whole blood/PBMC collection samples may be used for virologic analyses. PBMCs will be collected at baseline Day 1, Week 48, Week 96, or Withdrawal if prior to Week 96.
- q. Genetics sample should be collected only for patients who did not participate in the 201585(ATLAS) study (sample was previously collected and stored). Informed consent for genetic research must be obtained before sample collection. Sample may be collected at any visit after signing informed consent, but preferably at the Day 1 visit .
- r. One blood sample for CAB and RPV each to be collected at each PK timepoint. At Day 1, for participants from the ATLAS Q4W arm, PK samples are to be collected pre-dose relative to IM administration. At Week 4b, for participants randomized from SOC, Pre dose PK samples are to be collected: AFTER review of the PK diary to ensure that the samples are taken 20/28 hours after previous oral dose (diaries to be given at *Day 1 or W4a*); PRIOR to the final oral dose of CAB + RPV; PRIOR to the first IM injection.
- s. Only for Participants entering CAB + RPV Oral Treatment

- t. Participants switching to CAB LA + RPV LA will take final dose of oral lead-in regimen in the clinic at the Week 4b visit and begin injections. If possible, injections should be spaced approximately 2 cm from one another and from the site of any previous injection and or any injection site reaction. Bring RPV LA to approximately room temperature prior to injecting. Time and location of injection (right or left) as well as needle length used will be collected in the eCRF. The first injection can be performed as soon as central lab results become available and safety parameters are reviewed.
- u. All Patient Report Questionnaires/Surveys will be administered via paper instrument at the beginning of the visit before any other assessments are conducted and prior to administration of the eC-CSSRS. Conduct questionnaires/surveys at Withdrawal only if occurring at or prior to Week 48.
- v. The HIV-TSQc is to be administered to all participants transitioning from ATLAS and new participants transitioning from oral SOC. For participants transitioning from ATLAS, the version of the HIV-TSQc instrument to be administered will be based on the initial randomization arm at ATLAS Day 1.
- w. For patients randomized to oral SOC at Day 1 in ATLAS or new patients on SOC, the reasons for willingness to switch ART will be assessed at Day 1. For patients randomized to CAB LA + RPV LA Q4W in ATLAS, the reasons for willingness to continue long-acting ART in ATLAS-2M will be assessed at Day 1.
- x. Preference Questionnaire will be administered to all participants.
- y. Refer to Section 5.5 of the protocol for additional information on performing withdrawal assessments. HIV-1 RNA will be collected as Storage sample only if withdrawal assessments coincide with Week 52 or Week 100 (as per Section 5.5)
- z. Participants receiving one or more injections with CAB LA and/or RPV LA will be assessed with clinic visits at months 3, 6, 9 and 12 during the Long-Term Follow-Up Phase

Note: BP – Blood pressure, HR – Heart Rate, HDL – High Density Lipoprotein, LDL – Low Density Lipoprotein, PT Prothrombin Time, PTT Partial Thromboplastin Time, INR International normalized ratio

Procedure	Screening Visit ^a		Maintenance Phase																	Extension Phase	Withdrawal Assessments ^y	Long-Term Follow-up ^z					
	Day 1	Week																									
		Week 4A (Oral lead-in ONLY) ^b	Week 4B (Oral lead-in ONLY) ^b	8	9	16	24	32	40	41	48	56	64	72	80	88	96	100	Q8W After Week 96								
Symptom Directed Physical Exam and Medical Assessment ^e	X	X	X	X	X	X	X	X	X	X	X	X	X	X	X	X	X	X	X	X	X	X	X	X	X	X	
Weight, Height and BMI ^f		X									X							X								X	
Vital Signs (BP, HR, Temperature) ^g	X	X									X							X								X	
12-lead ECG ^h (triplicate at Day 1 pre-dose)	X	X									X							X								X	
CDC HIV-1 stage	X	X																									
HIV Associated Conditions		X	X	X	X	X	X	X	X	X	X	X	X	X	X	X	X	X	X	X	X	X	X	X	X	X	X
AEs, SAEs, Concomitant Medications	X _i	X	X	X	X	X	X	X	X	X	X	X	X	X	X	X	X	X	X	X	X	X	X	X	X	X	X
ISR Assessment for IM injection		X		X	X	X	X	X	X	X	X	X	X	X	X	X	X	X	X	X	X	X	X	X	X	X	X

Procedure	Screening Visit ^a		Maintenance Phase																	Extension Phase	Withdrawal Assessments ^y	Long-Term Follow-up ^z
	Day 1	Week																	Q8W After Week 96			
		Week 4A (Oral lead-in ONLY) ^b	Week 4B (Oral lead-in ONLY) ^b	8	9	16	24	32	40	41	48	56	64	72	80	88	96	100				
Columbia Suicide Severity Rating Scale (eC-SSRS) ^j	X	X		X	X		X	X	X	X		X	X	X	X	X	X	X			X	
Clinical chemistry and Hematology	X	X	X	X	X		X	X	X	X		X	X	X	X	X	X	X	X	X	X	X
Pregnancy Testing ^k	S	U	S	U	S		S	S	S	S		S	S	S	S	S	S	S	S	S	S	S
HIV-1 RNA and sample for storage (S) ^l	X	X		X	X		X	X	X	X		X	X	X	X	X	X	X	S	X	X	X
CD4+ cell count	X	X		X	X		X	X	X	X		X	X	X	X	X	X	X	X	X	X	X
CD8+ cell count		X						X				X						X			X	
Urinalysis ^m		X	X					X				X						X			X	
Fasting Labs Glucose, Cholesterol (Total, HDL and LDL) and Triglycerides ⁿ		X										X						X			X ^o	

Procedure	Screening Visit ^a		Maintenance Phase																	Extension Phase	Withdrawal Assessments ^y	Long-Term Follow-up ^z						
	Day 1	Week																										
		Week 4A (Oral lead-in ONLY) ^b	Week 4B (Oral lead-in ONLY) ^b	8	9	16	24	32	40	41	48	56	64	72	80	88	96	100	Q8W After Week 96									
Hepatitis B (HBsAg), Anti-HBc, and Anti-HBsAG, Hepatitis C (anti-HCV Ab)	X																											
PT/PTT/INR	X	X																										
PBMCs ^p		X								X								X								X		
Genetics sample ^q		X																										
PK sampling when transitioning from SOC ^r (S)=Storage only				X	X	X	X	X	X	X	X	S	S	S	S	S	X	S							X	S		
PK sampling when transitioning from CAB + RPV Q4W ^r (S)=Storage only		X			X	X	X	X	X	X	X	S	S	S	S	S	X	S							X	S		
Oral CAB and Oral RPV Dispensation ^s		X	X																									

Procedure	Screening Visit ^a		Maintenance Phase																	Extension Phase	Withdrawal Assessments ^y	Long-Term Follow-up ^z						
	Day 1	Week																										
		Week 4A (Oral lead-in ONLY) ^b	Week 4B (Oral lead-in ONLY) ^b	8	9	16	24	32	40	41	48	56	64	72	80	88	96	100	Q8W After Week 96									
IP accountability (Pill Counts)		X	X																									
IM treatment administration when transitioning from SOC ^t				X	X		X	X	X	X		X	X	X	X	X	X	X			X							
IM treatment administration when transitioning from CAB + RPV Q4W	X				X		X	X	X	X		X	X	X	X	X	X				X							
Patient Reported Outcomes ^u																												
HAT-QoL (short-form)		X						X				X															X	
HIV TSQs		X					X					X															X	
HIV TSQc ^v												X															X	
ACCEPT		X						X				X															X	

- h. A 12-lead ECG will be performed after resting in a semi-supine position for at least 5 minutes. ECGs will be performed pre-dose. For participants transitioning from ATLAS, the pre-dose Week 48 ECG can also serve as the ATLAS-2M Screening ECG. ECG pre-dose will be performed in triplicate at Day 1. A 2-hour post-dose ECG will also be performed at Days 1 and Week 48 for participants receiving CAB LA + RPV LA with an allowable window of ± 30 minutes.
- i. Only SAEs related to study participation or to a concomitantly administered ViiV/GSK product will be collected between obtaining informed consent and administration of study drug at Day 1.
- j. On Day 1, the eC-SSRS is to be administered prior to randomization. The eC-SSRS will preferably be completed at the beginning of the visit following administration of other PROs required prior to injections. The eC-SSRS is not required during the Withdrawal visit if withdrawal occurs during the Extension Phase.
- k. Women of childbearing potential only. SR=serum, UR=urine. Pregnancy events will be captured starting at Day 1 following initial exposure to study drug. Serum pregnancy test can substitute for urine pregnancy test if locally required but must be appropriately timed to confirm pregnancy status prior to randomization and first IM administration.
- l. Week 48 and Week 96 HIV-1 RNA retest (within 4 weeks) for results > 50 c/mL will be captured as unscheduled visit. Plasma for storage samples will be used for possible future analyses.
- m. A morning specimen is preferred. To assess biomarkers: urine albumin/creatinine ratio; urine protein/creatinine ratio; and urine phosphate. Urine phosphate results from visit 4a are not required by protocol to inform the safety review at visit 4b prior to receipt of initial CAB LA + RPV LA injections.
- n. An overnight fast is preferred; however, a minimum of a 6-hour fast is acceptable.
- o. Only collect if the Withdrawal visit occurs at Week 48 or Week 96.
- p. Whole blood/PBMC collection samples may be used for virologic analyses. PBMCs will be collected at baseline Day 1, Week 48, Week 96, or Withdrawal if prior to Week 96.
- q. Genetics sample should be collected only for patients who did not participate in the 201585(ATLAS) study (sample was previously collected and stored). Informed consent for genetic research must be obtained before sample collection. Sample may be collected at any visit after signing informed consent, but preferably at the Day 1 visit.
- r. One blood sample for CAB and RPV each to be collected at each PK timepoint. At Day 1, for participant from the ATLAS Q4W arm, PK samples are to be collected pre-dose relative to IM administration. injection. At Week 4b, for participants randomized from SOC, Pre dose PK samples are to be collected: AFTER review of the PK diary to ensure that the samples are taken 20/28 hours after previous oral dose (diaries to be given at Day 1 or W4a); PRIOR to the final oral dose of CAB + RPV; and PRIOR to the first IM injection. At Week 9 and 41, the PK samples should be collected 3 to 10 days after the Week 8 and Week 40 visits, respectively.
- s. Only for Participants entering CAB + RPV Oral Treatment
- t. Participants switching to CAB LA + RPV LA will take final dose of oral lead-in regimen in the clinic at the Week 4b visit and begin injections. If possible, injections should be spaced approximately 2 cm from one another and from the site of any previous injection and or any injection site reaction. Bring RPV LA to approximately room temperature prior to injecting. Time and location of injection (right or left) as well as needle length used will be collected in the eCRF. The first injection can be performed as soon as central lab results become available and safety parameters are reviewed.
- u. All Patient Report Questionnaires/Surveys will be administered via paper instrument at the beginning of the visit before any other assessments are conducted and prior to administration of the eC-CSSRS. Conduct questionnaires/surveys upon Withdrawal only if occurring at or prior to Week 48
- v. The HIVTSQc is to be administered to all participants transitioning from ATLAS and new participants transitioning from oral SOC. For participants transitioning from ATLAS, the version of the HIV-TSQc instrument to be administered will be based on the initial randomization arm at ATLAS Day 1

- w. For patients randomized to oral SOC at Day 1 in ATLAS or new patients on SOC, the reasons for willingness to switch ART will be assessed at Day 1. For patients randomized to CAB LA + RPV LA Q4W in ATLAS, the reasons for willingness to continue long-acting ART in ATLAS-2M will be assessed at Day 1.
- x. Preference Questionnaire will be administered to all participants
- y. Refer to Section 5.5 of the protocol for additional information on performing withdrawal assessments. HIV-1 RNA will be collected as Storage sample only if withdrawal assessments coincide with Week 52 or Week 100 (as per Section 5.5)
- z. Participants receiving one or more injections with CAB LA and/or RPV LA will be assessed with clinic visits at months 3, 6, 9 and 12 during the Long-Term Follow-Up Phase

Note: BP – Blood pressure, HR – Heart Rate, HDL – High Density Lipoprotein, LDL – Low Density Lipoprotein, PT Prothrombin Time, PTT Partial Thromboplastin Time, INR International normalized ratio

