Injection Site Reactions (ISRs)	
Clinical, experience to date has demonstrated ISRs occur in the majority of exposed participants treated with CAB LA but are generally mild (Grade 1) or moderate (Grade 2) and include events of pain, tenderness, erythema, or nodule formation of several days duration (median duration for individual events <1 week).
 
ISRs may occur more than once in an individual participant receiving multiple injections. Although some Grade 3 ISRs were reported, overall ISRs have been well tolerated and have not to date been associated with an excess of participants' withdrawal.
 
None of the ISRs reported to date have been serious.
	
 Administration advice will be given to minimize risk of poor administration technique giving rise to injection site reactions. Advice on care, monitoring, natural course, and treatment of ISRs is given in study documentation Advice will be given to participants on care of injection site on day/days immediately post administration, use of analgesia, compresses where appropriate. Participants will be closely monitored for ISRs particularly for signs of pain, tenderness, infections, erythema, swelling, induration, or nodules (granulomas or cysts) throughout the study. Complications of ISRs such as infections (abscess, cellulitis) and collections of fluid requiring drainage will be monitored

Potential Risk of Clinical Significance	Summary of Data/Rationale for Risk	Mitigation Strategy
		
 • Significant ISRs may be photographed and referred to a dermatologist for specialist advice.

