7.5.1. PK Sample Collection

Blood samples for evaluation of CAB (2mL each) and RPV (2 mL each) plasma PK concentrations will be collected from all participants as described in [Table 10](#).

For participants transitioning from oral SOC, at Week 4b PK samples should be collected within the window of 20-28 hours after the last oral dose of CAB + RPV was taken the day prior to the clinic visit. Participants will take their final dose of oral CAB + RPV in the clinic at Week 4b after the pre-dose PK sample.

These participants will be expected to complete a PK dosing diary card noting the date and time of the last three oral doses of IP prior to the scheduled clinic visits at Week 4b. The information from the diary card and the actual date and time of the PK samples will be recorded in the eCRF. Additionally, dosing information on the clinic day, including dosing and the actual date and time of the PK samples, must be recorded on the eCRF.

Plasma concentrations will be summarized and used to evaluate potential exposure-response relationships.

The timing of PK samples may be altered and/or PK samples may be obtained at additional time points to ensure thorough PK monitoring.

Table 10 CAB and RPV Plasma Pharmacokinetic Sample Schedule

Group	Analytes	Sample Times Relative to Dose
Participants receiving CAB LA + RPV LA Q4W injections	CAB and RPV	
Pre-Dose: Weeks 4b, 8, 16, 24, 32, 40, 48, and 96
 
A PK sample will be taken at Withdrawal.
 
PK samples for storage only:
 
Pre-dose: Week 12, 20, 28, 36, 44, 52, 56, 60, 64, 68, 72, 76, 80, 84, 88, 92, 100
 
Long-term follow-up Period (off-drug; storage sample)
 
Months 3, 6, 9, and 12

Participants receiving CAB LA + RPV LA Q8W injections	CAB and RPV	
Pre-Dose: Day 1*, Weeks 4b**, 8, 16, 24, 32, 40, 48, and 96
 
1 Week Post Dose: Week 9 and Week 41
 
A PK sample will be taken at Withdrawal
 
PK samples for storage only:
 
Pre-dose: Weeks 56, 64, 72, 80, 88, 100
 
LTFU Period (off-drug; storage sample)
 
Months 3, 6, 9, and 12
 
* Day 1 sample required only for those transitioning from ATLAS on Q4W injections.
 
**Week 4b sample required only for participants transitioning from oral SOC and requiring oral CAB + RPV Lead-in

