9.3.2.2. Other Secondary Endpoint Analyses

The primary analysis (Section 9.3.1) and key secondary efficacy analysis (Section 9.3.2.1) will be repeated at Week 96, with the only difference being a change in time point from Week 48 to Week 96 for determining the snapshot outcomes.

For the Week 24 planned analyses, the adjusted treatment difference in proportion of participants with plasma HIV-1 RNA ≥ 50 c/mL (FDA Snapshot algorithm, with 95% confidence interval) at Week 24 will be calculated using the methodology described in Section 9.3.1, but no formal test of non-inferiority will be performed at this early timepoint.

Proportion of participants with plasma HIV-1 RNA ≥ 50 c/mL and HIV-1 RNA < 50 c/mL (FDA Snapshot algorithm) at Week 24, Week 48 and Week 96 respectively, will be summarized using the Snapshot algorithm for the ITT-E population. Proportion of participants with confirmed virologic failures will also be summarized over time.

Absolute values and change from Baseline in CD4+ lymphocyte count will be summarized over time including Week 48 and Week 96.

The proportion of participants with HIV-1 RNA ≥ 50 c/mL based on the snapshot algorithm, will be summarized at Week 24, Week 48 and Week 96 by duration of prior CAB + RPV exposure (0 weeks, 1-24 weeks, >24 weeks).

The proportion of participants with HIV-1 RNA < 50 c/mL based on snapshot algorithm, will be summarized at Week 48 and Week 96 by duration of prior CAB + RPV exposure (0 weeks, 1-24 weeks, >24 weeks).

An observed case dataset, with no imputation for missing data, will be the primary dataset used for analysis of safety endpoints.

The proportion of participants reporting AEs will be tabulated for each treatment group. The following summaries of AEs will be provided:

- Incidence and severity of all AEs
- Incidence and severity of treatment related AEs
- Incidence and severity of AEs leading to withdrawal
- Incidence of SAEs

Changes from baseline in laboratory will be summarized by visit and treatment group including Week 48 and Week 96. In addition, the number and percentage of participants with graded laboratory toxicities (based on DAIDS categories) will be summarized by treatment group.

Further details for secondary efficacy, safety, and exploratory endpoint analyses will be included in the RAP.

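### Only the Q8W arm is seen 3 to 10 days after an injection (Weeks 9 and 41), so short-lived injection site reactions and AEs are ascertained unequally between arms and, within Q8W, before and after Week 48

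*Protocol*

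**What the plan says.** **Schedule.** Footnote r of the Q8W Time and Events Table (Protocol 7.1.2) states: "At Week 9 and 41, the PK samples should be collected 3 to 10 days after the Week 8 and Week 40 visits, respectively". Table 10 (7.5.1) lists one-week post-dose samples at "Week 9 and Week 41" for Q8W. For Q4W it lists pre-dose samples only, at "Weeks 4b, 8, 16, 24, 32, 40, 48, and 96", plus pre-dose storage samples. The Q4W footnote r has no Week 9/41 sentence; its timing rule ends at "PRIOR to the final oral dose of CAB + RPV; PRIOR to the first IM injection".

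**Assessments at those visits.** In the Q8W table the rows "AEs, SAEs, Concomitant Medications" and "ISR Assessment for IM injection" run without a gap through the Week 9 and 41 columns. Section 7.4.8 also requires the injection site to be checked at every visit.

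**Nature of the events.** Section 2.3.1 describes ISRs as including "nodule formation of several days duration (median duration for individual events <1 week").

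**Analysis.** Section 3 makes incidence and severity of AEs over time, including Weeks 24, 48 and 96, a secondary endpoint. Section 9.3.2.2 plans: "The proportion of participants reporting AEs will be tabulated for each treatment group". It makes no allowance for the different visit patterns.

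**The concern.** A reaction that resolves within days is most likely to be seen, measured and graded if someone looks within days. At Weeks 9 and 41 that happens in one arm only, and in that arm only before Week 48. A Q8W v Q4W difference in AE or ISR frequency or grade would then mix the effect of the regimen with the effect of looking. A change within Q8W across Week 48 would have the same problem.

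Section 4.4 gives the comparison of safety and tolerability between the regimens as one reason for the open-label design. It dismisses ascertainment bias on the ground that HIV-1 RNA is objective, then extends that conclusion to the study endpoints in general. The argument does not carry over to ISRs and reported AEs.

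**Working it through.** The protocol states no figure on this point to reproduce. The check is a count from the nominal schedule.

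**1. Are Weeks 9 and 41 more than PK visits?** In the Q8W table the eC-SSRS, chemistry/haematology and HIV-1 RNA rows are blank in exactly those two columns, while the AE and ISR rows are ticked straight through. The blanks show that the columns survived the conversion to text, so the AE and ISR ticks look deliberate. The AE and ISR rows carry 27 cells for 22 headings, so their exact alignment is inferred. Section 7.4.8 supports the same reading independently.

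**2. Injections followed by a visit 3 to 10 days later.** Injection weeks are taken from Sections 4.2.2.1 and 4.2.2.2:
- Q8W: Week 4b (from SOC) or Day 1 (from ATLAS), then 8, 16, 24, 32, 40, 48, 56, 64, 72, 80, 88.
- Q4W from SOC: Week 4b, then every 4 weeks from Week 8. Q4W from ATLAS: Day 1, then every 4 weeks.

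| Injections given | Q8W | Q4W from SOC | Q4W from ATLAS |
|---|---|---|---|
| Before Week 24 | 1 of 3 | 0 of 5 | 0 of 6 |
| Before Week 48 | 2 of 6 (33%) | 0 of 11 | 0 of 12 |
| Week 48 to before Week 96 | 0 of 6 | 0 of 12 | 0 of 12 |

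If the Week 48 injection is counted in the first period, the Q8W figure is 2 of 7.

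**3. Scheduled contacts.** For ATLAS rollovers after Day 1:
- Through Week 48: Q8W 8 (Weeks 8, 9, 16, 24, 32, 40, 41, 48), Q4W 12 (every 4 weeks). Ratio 12/8 = 1.5.
- Weeks 49 to 96: Q8W 6, Q4W 12. Ratio 12/6 = 2.0.

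Q8W contacts therefore fall from 8 to 6 while Q4W contacts stay at 12, and Q4W has more contacts in both periods.

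**4. What a one-week visit can see (illustration only).** The protocol gives only a median below one week. Assume exponential resolution with a median of 2 to 7 days, so the share still present at day t is 0.5^(t/median):
- Day 7: 0.5^(7/2) = 9% to 0.5^(7/7) = 50%.
- Day 28 (usual next Q4W visit): under 0.1% to 0.5^(28/7) = 6%.
- Day 56 (usual next Q8W visit): about 0% to 0.5^(56/7) = 0.4%.

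Direct observation of a resolving reaction is thus much likelier at Weeks 9 and 41 than at a pre-dose visit. This concerns only the Week 8 and Week 40 injections. The percentages describe what can be seen, not what is reported.

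**The case against.** A reader might infer more: that AE and ISR incidence must differ between the arms and must fall in Q8W after Week 48 simply because of the visit grid. The documents do not support that.

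- AEs are collected throughout treatment (7.4.3.1), and participants are asked about problems since the last contact (7.4.3.2). A resolved event is still reportable.
- Section 7.4.1 requires an ISR assessment before and after each injection, in both arms.
- Q4W has nearly twice the injections and more contacts, which works the other way. The longer Q8W recall interval, usually 8 v 4 weeks, also lowers Q8W reporting. Even that is not uniform: after the Week 4b injection, Q8W entrants from SOC return at Week 8.
- ISRs occur in most exposed participants (2.3.1), so many will already count in a per-participant proportion. Two extra visits may move it little.
- Safety is tabulated, with no test or margin, and Section 9.3.2.2 leaves further detail to the analysis plan.

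These points stand, and they rule out any claim about net direction or size. They do not remove the inequality. Recall replaces observation poorly for severity: the grading table in Appendix 2 grades erythema and induration partly by measured diameter or area, which cannot be recovered weeks later. A same-day check misses what develops afterwards. The unequal schedule is fixed in this protocol and not left to the analysis plan. The Week 24 analysis, meant to expedite submission (9.2.3.1), uses the Section 9.3.2.2 summaries and already contains one of the two visits.

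A second tempting step is to drop Week 9/41 events from the main comparison. That would remove real events from the investigational arm only, some of which would have been recalled at the next visit, and would make Q8W look safer.

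**Conclusion.** The point holds as differential ascertainment. Only Q8W has scheduled visits 3 to 10 days after an injection, they cover 2 of 6 injections before Week 48, and none is scheduled after Week 41. This may bias the between-arm comparison of AE and ISR incidence and severity, and the Q8W trend across Week 48. The effect on incidence cannot be sized, or its net sign derived, from the document. The primary endpoint and the HIV-1 RNA key secondary endpoint are not touched.

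The conclusion rests on two readings. The body of the Q4W Time and Events Table is not in the text at hand, so the absence of such visits in Q4W rests on Table 10 and the differing footnotes r. The amendment summary mentions Visits 9 and 41 under a heading covering both tables, but it describes changes and does not override Table 10. AE and ISR assessment at Weeks 9 and 41 rests on the unbroken table rows together with Section 7.4.8. The change is worth making because the affected comparison is a stated secondary objective and no new data are needed.

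**What to change.** In Section 9.3.2.2:

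1. Keep all events in the main AE and ISR tables.
2. Add a sensitivity analysis that sets apart events first recorded at the Week 9 or Week 41 visit and shows them separately.
3. Report ISRs per injection visit as well as per participant, by period: to Week 24, Weeks 24 to 48, Weeks 48 to 96.
4. State that Q8W has post-injection visits that Q4W does not, so that neither the arm difference nor the Q8W time trend is read without that in mind.

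The cost is analysis wording and one extra set of tables; no visits are added. The sensitivity analysis may understate Q8W, because some of the events set apart would otherwise have been recalled at the next visit. It should be read as a lower bound beside the main table: without the extra visits, the Q8W count would lie between the two. It does not correct for the 4- v 8-week contact interval, which the per-injection display only makes visible.
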